1.2 Schema

The trial design is depicted in [Figure 1](#).

Figure 1 Trial Schematic

MAO-B = monoamine oxidase B, PD = Parkinson's disease, MDS-UPDRS = Movement Disorder Society – Unified Parkinson's Disease Rating Scale, QD = once daily.
 R = randomize.

Note: The change from baseline to endpoint in the MDS-UPDRS Parts II and III combined score is the primary endpoint.

^aAdverse events and concomitant medications will be recorded. Nonserious adverse events will be followed through Week 31. Serious adverse events will be followed to resolution.

1.3 Schedule of Assessments

The Schedule of Assessments for the trial is shown in [Table 2](#). At each clinic visit, the assessments that are listed under “efficacy and other endpoint assessments” should be completed first, in the order listed, followed by the safety assessments, in the order listed.

Table 2 Schedule of Assessments

Trial Period:	Screen	Baseline	Treatment									Safety Follow-up ^a
			2	5	8	11	14	18	22	26	27 ^b	
Trial Week:	-4 to -1	1	2	5	8	11	14	18	22	26	27 ^b	31
Trial Day:	-31 to -1	1	14±3	35±3	56±3	77±3	98±3	126±3	154±3	182±3	189±3	217±3
Visit/Contact:	Visit 1	Visit 2	Visit 3	Visit 4	Visit 5	Visit 6	Visit 7	Visit 8	Visit 9	Visit 10	Visit 11 (EOT/ET)	Telephone ^c
Entrance and History												
Informed consent ^d	X											
Eligibility criteria	X	X										
Demography	X											
Psychiatric history ^e	←-----→											
Medical history ^e	←-----→											
Alcohol/illicit drug use inquiry	X											
Modified Hoehn and Yahr stage	X						X			X	X	
MoCA	X											
Randomization		X										
Efficacy and Other Endpoint Assessments												
MDS-UPDRS ^f	X	X		X	X	X	X	X	X	X	X	
CGI-S		X		X	X	X	X	X	X	X	X	
CGI-I ^g				X	X	X	X	X	X	X	X	
PGIC ^g				X	X	X	X	X	X	X	X	
PDQ-39		X								X	X	
Schwab and England ADL		X		X	X	X	X	X	X	X	X	
EQ-5D-5L		X					X			X	X	
Safety Assessments												
ESS		X	X	X	X	X	X	X	X	X	X	
QUIP-RS		X	X	X	X	X	X	X	X	X	X	

Table 2 Schedule of Assessments

Trial Period:	Screen	Baseline	Treatment										Safety Follow-up ^a
			2	5	8	11	14	18	22	26	27 ^b	31	
Trial Week:	-4 to -1	1	14±3	35±3	56±3	77±3	98±3	126±3	154±3	182±3	189±3	217±3	
Trial Day:	-31 to -1	1	14±3	35±3	56±3	77±3	98±3	126±3	154±3	182±3	189±3	217±3	
Visit/Contact:	Visit 1	Visit 2	Visit 3	Visit 4	Visit 5	Visit 6	Visit 7	Visit 8	Visit 9	Visit 10	Visit 11 (EOT/ET)	Telephone ^c	
C-SSRS ^h	X	X	X	X	X	X	X	X	X	X	X	X	
Physical/neurological examination ⁱ	X											X	
Weight	X	X										X	
Vital signs ^j	X	X	X	X	X	X	X	X	X	X	X		
12-Lead ECGs													
US sites													
Single ECG	X												
Three sets of triplicate ECGs ^k (-45, -30, and -15 min prior to first dose of IMP)		X											
One set of triplicate ECGs ^{k,l}		X		X		X	X		X		X		
Non-US sites													
Single ECG ^l	X	X		X		X	X		X		X		
One set of triplicate ECGs ^{k,l} prior to first dose of IMP		X											
						X ^v					X ^w		
Prior/concomitant medications	←-----→												
Adverse events ^m		←-----→											
Laboratoryⁿ													
Safety laboratory blood sample	X	X				X			X		X		
Prolactin level		X ^u									X ^u		
Serology (HIV, HbsAg, and HCV)	X												

Table 2 Schedule of Assessments

Trial Period:	Screen	Baseline	Treatment									Safety Follow-up ^a
Trial Week:	-4 to -1	1	2	5	8	11	14	18	22	26	27 ^b	31
Trial Day:	-31 to -1	1	14±3	35±3	56±3	77±3	98±3	126±3	154±3	182±3	189±3	217±3
Visit/Contact:	Visit 1	Visit 2	Visit 3	Visit 4	Visit 5	Visit 6	Visit 7	Visit 8	Visit 9	Visit 10	Visit 11 (EOT/ET)	Telephone ^c
Dipstick urinalysis ^o	X	X				X			X		X	
Serum pregnancy test ^p	X											
Urine dipstick pregnancy test ^p		←-----→										
Urine drug screen ^q	X	←-----→									X	
Plasma PK sample ^r		X		X		X	X		X		X	
Future biospecimen research blood sample ^s		X										
IMP Administration and Compliance^t												
Dispense IMP		X	X	X	X	X	X	X	X	X		
Assess IMP compliance			X	X	X	X	X	X	X	X	X	

Abbreviations: ADL = activities of daily living, CGI-I = Clinical Global Impression – Improvement, CGI-S = Clinical Global Impression – Severity of Illness, C-SSRS = Columbia-Suicide Severity Rating Scale, ECG = electrocardiogram, eCRF = electronic case report form, EQ-5D-5L = EuroQol 5 Dimension 5 Level, ESS = Epworth Sleepiness Scale, EOT = end of treatment, ET = early termination, HbsAg = hepatitis B surface antigen, HCV = hepatitis C virus, HIV = human immunodeficiency virus, IMP = investigational medicinal product, [REDACTED], MDS-UPDRS = Movement Disorder Society – Unified Parkinson’s Disease Rating Scale, MoCA = Montreal Cognitive Assessment, PDQ-39 = 39-Item Parkinson’s Disease Questionnaire, PGIC = Patient Global Impression of Change, PK = pharmacokinetic, QUIP-RS = Questionnaire for Impulsive-Compulsive Disorders in Parkinson’s Disease-Rating Scale.

- Subjects who prematurely discontinue from the trial or who are not eligible for or choose not to participate in the open-label extension trial (Protocol CVL-751-PD-004) are to participate in the 4-week Safety Follow-Up Period. Subjects who proceed into the open-label extension trial will go directly into that trial and will not complete the Safety Follow-Up Period.
- The assessments scheduled for the Week 27 visit are to be performed for any subject who prematurely discontinues from the trial.
- Contact with subjects via telephone call or other means of communication to check on their status.
- Informed consent must be obtained before any trial-related procedures are performed.
- Medical occurrences that begin before the start of IMP dosing but after obtaining informed consent will be recorded as medical and/or psychiatric history.
- MDS-UPDRS Parts I, II, and III will be conducted before the first dose of IMP at the Baseline Visit and at ~2 to ~6 hours after dosing (at home) at clinic visits during the Treatment Period.
- All responses will be relative to the subject’s condition at the Baseline Visit (Day 1) before the first dose of IMP.

- h. The “Baseline/Screening” C-SSRS form will be completed at the Screening Visit to determine eligibility. The “Since Last Visit” C-SSRS form will be completed at the Baseline Visit to ensure that the subject continues to qualify for the trial and at all visits after the Baseline Visit.
- i. Full physical and neurological examinations should be completed at the Screening Visit and at Week 27. The physical examination should include height at the Screening Visit only. Physical and/or neurological examinations can be done at any time point during the trial at the investigator's discretion.
- j. Duplicate measurements of blood pressure and heart rate will be obtained in supine (after 5 minutes of rest) and 1 measurement of blood pressure and heart rate will be obtained on standing (2 minutes after rising from supine to standing).
- k. A triplicate set of ECGs is 3 consecutive ECGs collected 1 to 2 minutes apart over a 5-minute period.
- l. The postdose ECGs (triplicate set for US sites at all visits and single for non-US sites at all visits) will be obtained at ~1 hour after administration of the first dose of IMP at the Baseline Visit just prior to the time of collection of the PK blood sample. ECGs at all postbaseline visits will be obtained just prior to the time of collection of the PK blood sample.
- m. All adverse events that are observed by trial personnel or volunteered by the subject in response to open-ended questioning will be recorded from the first dose of IMP through the end of the Safety Follow-up Period. Serious adverse events will be followed until resolution.
- n. Individual sites may require subjects to have COVID-19 testing done prior to randomization. COVID-19 testing may be performed after randomization per the principal investigator's discretion.
- o. Dipstick urinalysis results are not to be recorded on the eCRFs; any clinically significant abnormality should be captured as an adverse event.
- p. For women of childbearing potential only. All positive urine dipstick pregnancy tests must be confirmed by a serum test. Pregnancy tests can be performed at any time during the trial at the discretion of the investigator. Female subjects with exclusively the same sex partners may not be required to have pregnancy tests per investigator discretion; confirmation with the medical monitor is required.
- q. A urine drug screen is required at screening (see exclusion criteria for exclusions based on the urine drug screen) and may be obtained at other times, at investigator discretion, if use of prohibited drugs is suspected.
- r. PK samples will be collected ~1 hour after administration of the first dose (Day 1) and at the clinic visits at the end of Weeks 5, 11, 14, 22, and 27 just after ECG acquisition at each time point. The date and time of the most recent dose, the dose amount, and the time of the blood draw will be recorded.
- s. Future biospecimen research sample is optional and is to only be collected if signed consent is obtained from the subject.
- t. The first dose of IMP (at the Baseline Visit) will be taken in the clinic; all other doses will be taken on an outpatient basis. Subjects will be instructed to bring their IMP to each clinic visit. Compliance will be assessed through self-reporting by the subject and by tablet count.
- u. Prolactin results will be blinded.

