5.4 Screen Failures

Screen failures are defined as subjects who consent to participate in the clinical trial but who are not subsequently randomized to treatment in the clinical trial. A minimal set of screen failure information is required to ensure transparent reporting of screen failure subjects to meet the Consolidated Standards of Reporting Trials (CONSORT) publishing requirements and to respond to queries from regulatory authorities. Minimal information includes demography, screen failure details, and eligibility criteria.

Individuals who do not meet the criteria for participation in this trial (screen failure) at screening may be rescreened once at the discretion of the investigator and after consultation with the sponsor unless screen failure is due to a positive urine drug screen for illicit substances other than tetrahydrocannabinol (THC) ([Section 5.2, exclusion 18](#)). Subjects who have a positive urine drug screen for THC at screening may be rescreened once and randomized into the trial if the repeat urine drug screen is negative for THC, and the subject agrees to abstain from THC use throughout the duration of the trial. Rescreened subjects will be assigned a new subject number.

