6.5.2 Prohibited Medications Before the Trial

Subjects must agree to discontinue use of all prohibited medications in accordance with predefined washout periods, as shown in [Table 6](#).

Table 6 List of Medications Prohibited Before the Trial

	Medication	Washout Period
1.	Moderate or strong CYP3A4 inducers or CYP3A4 inhibitors (refer to Section 10.6 [Appendix 6] for examples), except for topical administration	--
2.	Amantadine	>14 days before Baseline Visit
3.	L-Dopa or a dopamine agonist if exposure was \geq 3 months in total or within 2 months of the Baseline Visit	--
4.	Anticholinergic drugs if exposure was >1 month	--
5.	Anticholinergic drugs if exposure was <1 month	>14 days before Baseline Visit
6.	COMT inhibitors, droxidopa, zonisamide, or istradefylline	--
7.	Varenicline	>14 days before Baseline Visit
8.	Nonselective MAO inhibitors, methyldopa, reserpine, or tricyclic antidepressants	>2 months before Screening Visit
9.	Dopamine antagonists, such as neuroleptics/antipsychotics (eg, phenothiazines, butyrophenones, thioxanthenes), including haloperidol, trimethobenzamide, or domperidone for nausea/vomiting, metoclopramide, and quetiapine for insomnia	>14 days before Baseline Visit
10.	Atypical antipsychotics, mood stabilizers (lithium or anticonvulsants), or prescription stimulants (amphetamine derivatives, methylphenidate, bupropion, phentermine, phenylpropanolamine modafinil, mazindol) Note: use of certain anticonvulsants (eg, pregabalin) for medical reasons unrelated to seizures or psychiatric mood stabilization may be allowed after discussion with and approval by the medical monitor.	>14 days before Baseline Visit (1 full cycle for long-acting depot antipsychotics)
11.	Sedatives, hypnotics, antidepressants, or anxiolytics	No washout is required if dose has been stable for >90 days before the Baseline Visit; washout of >14 days if dosing was started or dose was changed ≤ 90 days before the Baseline Visit
12.	MAO-B inhibitors if use was initiated ≤ 90 days before Baseline Visit	>14 days before Baseline Visit
13.	Other investigational medications	>60 days before Screening Visit

Abbreviations: COMT = catechol-O-methyltransferase, CYP = cytochrome P450, ICF = informed consent, L-Dopa = levodopa, MAO = monoamine oxidase.

-- Not applicable. Any prior use is prohibited.

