8.4 Adverse Events, Serious Adverse Events, and Adverse Events of Special Interest

The definitions of an AE and SAE are provided in [Section 10.3](#) (Appendix 3). The AESI for this trial are defined in [Section 8.4.6](#).

Adverse events will be reported by the subject (or, when appropriate, by a caregiver, surrogate, or the subject's legally authorized representative, as defined per local regulations). The investigator and any qualified designees are responsible for detecting, documenting, and recording events that meet the definition of an AE, SAE, or AESI and remain responsible for following up SAEs/AESI that are considered related to the trial intervention or trial procedures or that cause the subject to discontinue IMP (see [Section 7.3](#)).

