8.4.1 Time Period and Frequency for Collecting AE and SAE/AESI Information

All AEs and SAEs/AESIs will be recorded from the first dose of IMP until follow-up contact at the time points specified in the Schedule of Assessments ([Table 2](#)).

Medical occurrences that begin before the start of IMP dosing but after obtaining informed consent will be recorded as medical and/or psychiatric history.

All SAEs/AESI will be recorded and reported to the sponsor or designee immediately and under no circumstance should this exceed 24 hours, as indicated in [Section 10.3](#) (Appendix 3). The investigator will submit any updated SAE/AESI data to the sponsor within 24 hours of it being available.

Investigators are not obligated to actively seek AEs, SAEs, or AESI after conclusion of the trial participation. However, if the investigator learns of any SAE, including a death, at any time after a subject has been discharged from the trial, or AESI and he/she considers the event to be reasonably related to the trial intervention or trial participation, the investigator must promptly notify the sponsor.

8.4.2 *Method of Detecting AEs and SAEs/AESI*

The method of recording, evaluating, and assessing causality of AEs and SAEs/AESI and the procedures for completing and transmitting SAE/AESI reports are provided in [Section 10.3](#) (Appendix 3).

Care will be taken not to introduce bias when detecting AEs and/or SAEs/AESI. Open-ended and nonleading verbal questioning of the subject is the preferred method to inquire about AE occurrences.

8.4.3 *Follow-up of AEs and SAEs/AESI*

After the initial AE/SAE/AESI report, the investigator is required to proactively follow each subject at subsequent visits/contacts. All SAEs/AESI will be followed until resolution, stabilization, the event is otherwise explained, or the subject is lost to follow-up (as defined in [Section 7.4](#)). Further information on follow-up procedures is given in [Section 10.3](#) (Appendix 3).

8.4.4 *Regulatory Reporting Requirements for SAEs/AESI*

Prompt notification by the investigator to the sponsor of an SAE/AESI is essential so that legal obligations and ethical responsibilities towards the safety of subjects and the safety of a trial intervention under clinical investigation are met.

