10.3.1 Definition of AE

Table 12 Definition of AE

AE Definition

• An AE is any untoward medical occurrence in a patient or clinical trial subject, temporally associated with the use of trial intervention, whether or not considered related to the trial intervention.• NOTE: Signs and symptoms and/or abnormal laboratory test result indicating a common underlying pathology/diagnosis should be reported as a single AE.

Abbreviation: AE = adverse event.

Table 13 Events Meeting the AE Definition

Events Meeting the AE Definition

• Any abnormal laboratory test results (hematology, clinical chemistry, or urinalysis) or other safety assessments (eg, ECG, radiological scans, vital signs measurements), including those that worsen from baseline, considered clinically significant in the medical and scientific judgment of the investigator.• Exacerbation of a chronic or intermittent pre-existing condition including either an increase in frequency and/or intensity of the condition.• New conditions detected or diagnosed after trial intervention administration even though it may have been present before the start of the trial.• Signs, symptoms, or the clinical manifestations of a suspected drug-drug interaction.• Signs, symptoms, or the clinical manifestations of a suspected overdose of either trial intervention or a concomitant medication. “Lack of efficacy” or “failure of expected pharmacological action” per se will not be reported as an AE or SAE/AESI. Such instances will be captured in the efficacy assessments.

Abbreviations: AE = adverse event, AESI = adverse event of special interest, ECG = electrocardiogram, SAE = serious adverse event.

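### A serious event between consent and first dose that is caused by a required washout or screening procedure is not recorded as an SAE and has no 24-hour report to the sponsor

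*Protocol*

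**What the plan says.** Two places in the Protocol set the rule for the interval between consent and first dose. Footnote e to Table 2 (Section 1.3) reads: "Medical occurrences that begin before the start of IMP dosing but after obtaining informed consent will be recorded as medical and/or psychiatric history". Section 8.4.1 repeats it and gives the start of recording for serious events as well as ordinary ones: "All AEs and SAEs/AESIs will be recorded from the first dose of IMP until follow-up contact". Footnote m to Table 2 agrees that adverse events "will be recorded from the first dose of IMP through the end of the Safety Follow-up Period".

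Expedited reporting applies to events already classed as SAEs or AESIs: "All SAEs/AESI will be recorded and reported to the sponsor or designee immediately and under no circumstance should this exceed 24 hours" (Section 8.4.1).

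For entry, Section 6.5.2 states: "Subjects must agree to discontinue use of all prohibited medications in accordance with predefined washout periods". Table 6 gives a washout of more than 14 days before Baseline for several classes. These include amantadine, dopamine antagonists, atypical antipsychotics, mood stabilizers, MAO-B inhibitors started within the last 90 days, and antidepressants or anxiolytics started or changed within the last 90 days.

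For subjects who fail screening, Section 5.4 says: "Minimal information includes demography, screen failure details, and eligibility criteria".

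**The concern.** A subject who stops a medicine in order to qualify takes on a risk that exists only because of the trial, before any IMP is given. If stopping leads to a hospitalisation, the sponsor would want to know quickly, because other subjects at other sites may be starting the same washout. Under the present text the investigator has no instruction to treat that event as serious or to report it within a day. It is filed with the subject's background history, or the subject fails screening and falls under a minimum data set with no item for events. A recurring problem during washout could therefore be noticed late while recruitment continues. What is at stake is subject protection and the completeness of safety reporting. The treatment comparison is not affected.

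**Working it through.** The plan gives no figure to reproduce, so the check is a reading of the rules in sequence, with one piece of timing arithmetic.

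1. **Recording window.** Footnotes e and m and Section 8.4.1 agree: history before the first dose, AEs and SAEs from the first dose. None of the three excepts serious events, or events caused by a procedure or washout.

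2. **Definitions.** Section 10.3.1 states: "An AE is any untoward medical occurrence in a patient or clinical trial subject, temporally associated with the use of trial intervention". Section 10.3.2 adds that an event which is not an AE cannot be an SAE, whatever its seriousness. Before the first dose there has been no use of trial intervention, so a pre-dose event is excluded by definition as well as by date. Changing Section 8.4.1 alone would leave this second barrier in place.

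3. **Can a washout fall inside the window?** Table 2 places screening at Day -31 to Day -1; the text of Section 4.1.1 gives a maximum of 4 weeks, or 28 days. The relevant Table 6 washouts are just over 14 days before Baseline. Then 31 - 14 = 17 days, or 28 - 14 = 14 days, remain to spare. On either figure the washout can start after consent and finish before the first dose. Table 2 also requires consent before any trial-related procedure, so all screening procedures lie in the same window.

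4. **Which Table 6 rows do not count?** Rows marked with dashes bar any prior use and involve no washout. Rows counted back from the Screening Visit (more than 2 months, more than 60 days) may be over before consent. Antidepressants and anxiolytics at a stable dose for more than 90 days need no washout.

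5. **Does any other text supply the missing route?**
   - Section 8 asks that immediate safety concerns be discussed with the sponsor, in order to decide whether trial intervention continues. It creates no SAE record and no reporting deadline.
   - Section 8.4 says investigators "remain responsible for following up SAEs/AESI that are considered related to the trial intervention or trial procedures". This is a duty to follow up events that are already SAEs; it does not move the start of recording.
   - The Section 8.4.1 clause on events learned of after discharge also needs an event that already qualifies.
   - Section 10.2 (laboratory abnormalities), footnote o (dipstick findings) and SAP 5.14.1 (AEs before study treatment, kept for listings) mention AEs without a first-dose limit or expect pre-dose AEs. They fit poorly with the first-dose rule and should be reconciled with it, but none gives a reporting route for harm from a washout or procedure.

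No route remains under which such an event is an SAE with a 24-hour report.

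**The case against.** The strongest reply is that the first-dose rule is deliberate and coherent. The footnotes, Section 8.4.1 and the AE definition agree with one another, and the amendment history shows that the rule was introduced on purpose in Version 3.0. That stands, and it is a reason to leave routine pre-dose events as they are. It does not explain why serious harm from the protocol's own entry requirements should be treated in the same way.

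A reader might infer that these events never reach the sponsor at all. The documents do not support that:

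- Medical and psychiatric history is coded, summarised by arm and listed (SAP 5.7).
- Screen-failure details are kept (Section 5.4) and reasons for failure are logged (Section 8.1).
- The C-SSRS at Baseline would pick up suicidal behavior in a subject who attends.
- Section 8 invites discussion of immediate safety concerns.
- SAP 5.1 plans listings for everyone who signs consent, although SAP 9.4 says listings cover randomized subjects.

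What is missing is SAE status and the deadline.

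A reader might also see a contradiction in the Section 8.4 reference to procedures. There is none: that duty keeps its full meaning for blood draws and ECGs after the first dose.

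Finally, it is tempting to size the gap by multiplying the number of subjects by the length of screening. That would count everyone for the full window, whether or not they stop a medicine, and would apply no event rate. It does not measure this gap.

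The case that exposure is limited has force. Eligibility criteria exclude recent psychosis or hallucinations, serious suicide risk, and subjects likely to need prohibited medication during the trial. The screening procedures themselves are low risk: questionnaires, ECG, vital signs, examinations, and blood and urine samples.

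**Conclusion.** The point holds in this narrow form: a serious event between consent and first dose that is caused by a protocol-required procedure, or by a Table 6 washout falling after consent, is not recorded as an SAE and need not be reported to the sponsor within 24 hours. This follows from rules the Protocol states outright, not from missing detail.

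The number of subjects who would need such a washout is not given, and no event rate can be taken from the documents. I expect the number of events to be small. The conclusion assumes that at least some subjects stop a listed medicine after signing consent, which the timing permits, and that no manual unavailable here adds a reporting route. Sample size, type I error, efficacy estimates and TEAE summaries are unaffected. It is a safety-reporting improvement worth making because it is cheap.

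**What to change.** In Section 8.4.1 and in footnotes e and m of Table 2, state that from signing of consent to first dose, any serious event the investigator considers related to a protocol-required procedure or washout is recorded and reported to the sponsor within 24 hours, and that this includes subjects who go on to fail screening. Amend Sections 10.3.1 and 10.3.2 so that the AE and SAE definitions allow for these events. Add a matching line to Section 5.4 so that they form part of the screen-failure data.

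In the SAP, list these events separately and keep them out of the TEAE tables. SAP 3.2.3.2 already starts TEAEs at initiation of IMP, so those summaries do not change. All other pre-dose events stay as medical or psychiatric history. At the same time, align Section 10.2, footnote o and SAP 5.14.1 with whatever start date is kept for routine AEs.

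The cost is some protocol and SAP wording, one eCRF flag and a few extra reports. No washout, dose or eligibility rule is touched.
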